Clinical Research Program

Project name: Prospective Validation of Pathology-based Artificial Intelligence Diagnostic Model for Lymph Node Metastasis in Prostate Cancer

Bidding organization: Sun Yat-sen Memorial Hospital

Version No.: V1.1

Version date: January 31, 2025

Project Manager: [name]

NCT number: NCT06253065

I. Summary of the research program

Lymph node metastasis is a prevalent mode of spread in prostate cancer, and accurate postoperative pathological lymph node staging holds significant implications for subsequent treatment and prognosis. However, the existing approach to pathological assessment relies on manual image review by pathologists, leading to low diagnostic efficiency and potential missing diagnosis of micrometastases. In our prior study, we addressed this challenge by developing a deep learning-based AI diagnostic model (named ProCaLNMD) for prostate cancer lymph node metastasis detection. The model demonstrated promising results in retrospective validation.

This study, framed as a diagnostic trial without intervention, seeks to enroll patients who have undergone radical prostatectomy with pelvic lymph node dissection for prostate cancer, possessing comprehensive clinical and pathologic data. The study is planned to enroll approximately 200 patients in our center, with 2,000 images of corresponding pathological lymph node sections from these patients, and gather the relevant clinicopathological data to prospectively validate the performance of the AI model.

II. Background of the study

Globally, prostate cancer ranks as the second most common malignant tumor in men, surpassed only by lung cancer. It stands out as the predominant malignant tumor within the male genitourinary system and holds the highest incidence in the male urogenital system¹. Lymph node metastasis serves as a prevalent way of its spread, and the identification of regional lymph node metastasis plays a pivotal role in guiding subsequent postoperative treatment and determining prognosis. Despite its significance, achieving accurate pathologic lymph node staging remains a formidable challenge, particularly when dealing with micrometastases. The inherent characteristics of these

lesions, such as small diameters, minimal lesion involvement, and the limited resolution of the human eye, can contribute to missing diagnoses. Conventional pathology has demonstrated restricted sensitivity in detecting micrometastases, posing an increased risk of cancer progression and potential delays in implementing adjuvant therapy. While immunohistochemistry and molecular markers can enhance the detection of micrometastases, they are expensive and not routinely used².

In recent years, the widespread adoption of artificial intelligence in digital pathology diagnosis has been facilitated by advancements in whole slide imaging technology, coupled with increased computational power and data storage capacity³. This technology has the capability to extract image features from pathological images that may be missed by the human eye, enabling accurate disease diagnosis, prognosis assessment, and treatment predictions. Literature reports highlight the successful construction of a deep learning-based AI diagnostic model for lymph node metastasis in breast cancer. The diagnostic performance of this model has been shown to rival that of experts⁴. Our previous study involved the development and retrospective validation of a deep learning-based AI diagnostic model for pathological lymph node staging in prostate cancer. This model utilized postoperative resected lymph node pathological images, complemented by the construction of AI-assisted software for pathological lymph node reading. In retrospective validation, the AI system demonstrated strong performance, with diagnostic sensitivity comparable to senior pathologists. This capability holds promise in assisting physicians by reducing missed diagnoses of micrometastases and enhancing diagnostic accuracy and efficiency. However, there remains a need for a well-established prospective validation to assess the diagnostic proficiency and practical application of this model in a real clinical setting.

[figure not shown]
III. Research purpose

To evaluate the diagnostic performance and application value of the pre-developed AI diagnostic model for prostate cancer lymph node metastasis detection in real clinical

settings.

IV. Research design

The study is a prospective diagnostic trial and the flow chart of the study design is shown below:

V. Research Program and Technical Route

(i) Study population

Approximately 200 patients with prostate cancer in our center will be prospectively enrolled, and their lymph node pathological slides will be collected after pelvic lymphatic dissection.

1. Inclusion criteria

- (1) Patients with prostate cancer who underwent radical prostatectomy and pelvic lymph node dissection;
- (2) Complete clinical and pathological information.

2. Exclusion criteria

- (1) Presence of other tumors with pelvic lymph node metastases;

[figure not shown]
- (2) Low quality images;
- (3) Patients refusing to participate in this research.

(ii) Data collection

1. Collect clinical and pathological data of the enrolled patients;
2. Digital whole slide images (WSI) of the patient's lymph node histopathological sections will be generated using a digital scanner. Low-quality images were eliminated from consideration. Approximately 10 lymph node pathology slides will be acquired from each patient who underwent radical prostatectomy with pelvic lymphatic dissection for prostate cancer, resulting in the collection of around 2000 pathologic lymph node images.

(iii) AI algorithm models

Capture the thumbnail of the Whole Slide Image (WSI) and delineate the organizational block region for classification. Employ a sliding window approach to traverse the tissue block region, generating patches of size $3*2028*2048$ by moving from top to bottom and left to right. Input all the patches into the RegNetY_40 model, obtain the segmentation prediction probability for each patch, and convert the probabilities to 8-bit format (0~255). Set the probability threshold at 254, classifying pixels with a probability value equal to or greater than 254 as Tumor pixels. Calculate the count of tumor pixels within the WSI, using a number threshold of 0. If the number of pixels in the cancer category within the WSI is greater than 0, classify the WSI as positive (indicating the presence of tumor lymphatic metastasis); otherwise, classify it as negative (indicating the absence of tumor lymphatic metastasis). The flowchart is shown below:

(iv) Indicators for evaluating the results of the study

1. Accuracy: Ratio of the combined number of true-positive and true-negative cases predicted by the AI model to the total number of cases tested.
2. Sensitivity: Ratio of positive cases identified by the AI model to the number of positive cases confirmed by the gold standard.
3. Specificity: Ratio of negative cases identified by the AI model to the number of negative cases confirmed by the gold standard.

(v) Informed consent

The study, titled "Prospective Validation of Pathology-based Artificial Intelligence Diagnostic Model for Lymph Node Metastasis in Prostate Cancer," is a diagnostic trial devoid of interventions. Prior to the enrollment of each patient, and before they undergo the scheduled procedure, the researcher provides a comprehensive introduction to the protocol, purpose, procedures, associated costs, potential benefits, possible risks, confidentiality measures, and the patient's rights within the trial. Subsequently, an informed consent form is distributed to the patient, and enrollment in the study occurs only after the patient has signed the informed consent.

(vi) Ethical requirements

The study adhered to the guidelines outlined in the Good Clinical Research Practice

and the Declaration of Helsinki. Before the commencement of the trial, the protocol received approval from the hospital's Ethics Committee. In the event that a revision to the protocol becomes necessary during the study, the updated version must be resubmitted for review by the Ethics Committee. The investigator is required to await approval from the Ethics Committee before implementing any modifications to the protocol.

In the course of this study, clinical data and personal information from research participants will be gathered for scientific research purposes, potentially implicating the privacy rights of the patients. To safeguard confidentiality, participants and data analysts involved in the study will be required to sign a confidentiality agreement. This agreement ensures that personal information and disease-related details of patients will not be disclosed to any individuals or organizations unrelated to the study. Stringent measures will be implemented to manage the collected patient data in a unified manner, mitigating the risk of personal information leakage.

VI. Security evaluation

None.

VII. Data collection and management

1. Study subjects

It is planned to prospectively enroll about 200 consecutive prostate cancer patients who need to undergo radical prostatectomy and pelvic lymph node dissection in our center from January 2024 to December 2025 for the validation of the AI model.

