1.2 Exclusion criteria

- (1) Presence of other tumors that metastasize to the pelvic lymph nodes;
- (2) Low quality images;
- (3) Patients refusing to be enrolled.

2. Data collection

2.1 Clinical and pathologic data were collected from the enrolled patients;

2.2 Digitally scanning the pathologic histological sections of the patient's postoperatively resected lymph nodes. Approximately 10 lymph node pathology slides will be acquired from each patient, resulting in the collection of around 2000 pathological lymph node images.

VIII. quality management program

(i) Measures to improve consistency of observations

1. Every researcher involved in this project must undergo pre-study training to ensure a comprehensive understanding of the research program and the specific implications of its indicators. This initiative aims to enhance both intra-observer and inter-observer consistency among the clinical research data collectors, ultimately ensuring the reliability of the clinical research conclusions.

2. Each clinical research unit is expected to appoint an individual responsible for regularly monitoring the progress of the clinical research. This designated person will meticulously verify data and records to maintain the accuracy and integrity of the research findings.

(ii) Measures to ensure subject compliance

The subject profile must be strictly controlled for variables through the following measures:

1. Consistent involvement of physicians in clinical studies within each unit.
2. Researchers are required to diligently elucidate the informed consent of enrolled patients. This ensures a comprehensive understanding of the trial study's processes and the associated obligations of cooperation, thereby fostering active participation in the trial.

(iii) Monitoring of clinical trials

Competent monitors, designated by the sponsor, are tasked with conducting routine monitoring activities both before, during, and after the trial. This ensures strict adherence to all aspects of the research protocol and meticulous scrutiny of the source material.

IX. Pre-assessment of project risk benefits and risk control plan

Potential Benefits: Expected to assist pathologists in reducing missed diagnosis of lymph node micrometastases; No potential risk.

X. References

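### Poor-quality scans are dropped after enrolment under a rule filed among patient exclusions, so the results cover readable scans only, and the decision to drop is not required to be blind

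*Protocol*

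**What the plan says.** Protocol V(ii), item 2, describes whole-slide scanning and then states: "Low-quality images were eliminated from consideration". Both exclusion lists, V(i) 2 and VII 1.2, carry "Low quality images" as item (2). It sits between a criterion on other tumors and one on refusal, both of which concern patients.

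VII 2.2 describes scanning a second time ("Digitally scanning the pathologic histological sections of the" ...) and does not mention dropping images.

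On timing, V(v) places consent "Prior to the enrollment of each patient, and before they undergo the scheduled procedure", and V(i) has the slides collected after the dissection. VII 1 plans to "prospectively enroll about 200 consecutive prostate cancer patients".

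V(iv) defines three indicators. Accuracy is taken relative "to the total number of cases tested". Sensitivity is taken relative to the "number of positive cases confirmed by the gold standard", and specificity to the "number of negative cases confirmed by the gold standard". V(iii) classifies each whole-slide image, and any tumor pixel makes it positive.

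Sections II and III give the aim as assessing the model's diagnostic performance and practical value in a real clinical setting.

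**The concern.** Image quality is known only after surgery, sectioning and scanning, so the rule cannot select patients at entry. In practice it removes slides that belong to patients already enrolled as part of a consecutive series.

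Two things are at stake. First, a laboratory using the model will meet unreadable scans, and for those slides the AI gives no usable answer. Estimates on readable scans alone answer a narrower question than the one the protocol poses, and the protocol does not ask for the number dropped. Second, the removal rule contains no requirement that the person judging quality be unaware of the AI output or the reference diagnosis. A slide on which the two disagree could therefore be looked at again and set aside as poor. The protocol does not suggest that this happens, but it does not prevent it.

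**Working it through.** **Sequence in the protocol.** Consent and enrolment (V(v)), then surgery, then slides (V(i)), then scanning and removal of poor images (V(ii)), then AI classification of each image (V(iii)). Removal therefore always follows enrolment.

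**The plan's own figure.** About 200 patients x about 10 slides = 2,000 images, which agrees with V(ii) and VII 2.2. This product leaves no allowance for dropped images.

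**Inputs that the protocol does not give (assumed).**
- q, the share of images dropped: 1% to 5%, taken as equal in gold-standard positive and negative slides. Of 2,000 images this is 2,000 x 0.01 = 20 to 2,000 x 0.05 = 100.
- s, the share of retained slides classified correctly: 0.95.
- b, the share of dropped slides that the AI would have classified correctly: unknown, so the full range 0 to 1.

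**Formula.** On retained slides the figure is s. On all slides it would be s(1 - q) + qb. The shift caused by dropping images is the difference:

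s - [s(1 - q) + qb] = q(s - b)

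**Results, in percentage points, for sensitivity or specificity at slide level.**

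| q | b = 1 | b = 0 |
|---|---|---|
| 1% | 0.01 x (0.95 - 1) = -0.05 | 0.01 x 0.95 = +0.95 |
| 2% | 0.02 x (0.95 - 1) = -0.10 | 0.02 x 0.95 = +1.90 |
| 5% | 0.05 x (0.95 - 1) = -0.25 | 0.05 x 0.95 = +4.75 |

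The shift is zero when b = s. It is positive, so that the reported figure is too favorable, whenever the AI does worse on poor images than on good ones.

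**Direction.** b need not be the same in positive and negative slides. Because one tumor pixel makes a slide positive, an artefact could trigger a positive call. If poor images were always called positive, b would be 1 among positive slides and 0 among negative ones. At q = 5%, dropping them would then change sensitivity by -0.25 points and specificity by +4.75. If poor images instead hid small deposits and were always called negative, the two shifts would change places. The protocol gives no basis for choosing between these.

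**The case against.** The case for leaving the text alone has several parts.

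- **The unit is clear.** V(ii) and both lists speak of images, and the model classifies images. A reader might infer from the position in the lists that one poor scan removes the whole patient. The wording does not say so, and the fault is one of placement. This stands. The flow chart, which is missing from the text reviewed, may also show the level of exclusion.
- **The denominators are not in real conflict.** A reader might infer from V(iv) that a dropped image with a reference diagnosis stays in sensitivity and specificity but leaves accuracy. That is strained. An image taken out of consideration naturally leaves all three indicators, and the sensitivity and specificity definitions are the usual textbook ones. This stands too.
- **Other criteria also act late.** Having undergone surgery and having complete data can likewise be confirmed only after the operation, so timing alone does not single out image quality. This is true. What distinguishes this item is that it concerns a slide rather than a person, and that its removal narrows what is being estimated.
- **Handling of unreadable scans can sit in the analysis plan.** That plan is not at hand, and the lack of a second analysis in the protocol is no fault in itself. The objection does not reach the rule the protocol itself states, its place among patient exclusions, or its fit with the stated aim.
- **Counting unusable scans as errors mixes scanner failure with model error.** This is fair, and is why that analysis should be supplementary.

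**Conclusion.** The point holds as a modest but worthwhile correction. The plan as written drops slides of enrolled, consecutive patients, restricts all three indicators to readable scans in a study meant to reflect real clinical use, and does not require the decision to be blind.

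A reader might go further and conclude that the reported performance will be inflated. The protocol does not support that. It gives no rate of poor images, no expected performance and no information on how the AI behaves on poor images. Under the assumed 95% on retained slides, the slide-level shift lies between -0.05 and +0.95 points if 1% of images are dropped, and between -0.25 and +4.75 points if 5% are. The upper ends require the AI to be wrong on every dropped image. An upward shift is plausible if the model does worse on poor scans, but neither its sign nor its size is established. No shift in patient-level sensitivity is claimed either, since the protocol defines no patient-level AI call.

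**What to change.** Take the image-quality item out of the exclusion lists in V(i) 2 and VII 1.2, and state one image-level rule in both V(ii) and VII 2.2, for example:

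*For slides not yet processed, usability of an image is judged without knowledge of the AI output or the gold standard. An unusable image is logged as non-evaluable together with its gold-standard status, and its patient remains in the study. For slides already processed, the log records, where this can be recovered, whether removal came before or after the AI output was known.*

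Report the non-evaluable rate. Within each analysis, give sensitivity, specificity and accuracy on one common set of images: evaluable images as the main analysis, and all images, with non-evaluable ones counted as not correctly classified, as a supplementary analysis.

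**Cost.** A log, a little more analysis, and an amendment that V(vi) sends to the Ethics Committee. The supplementary figures will be lower than the main ones: by 0.95 points at 1% non-evaluable and 4.75 points at 5%, under the assumptions above (the b = 0 column). Blind judgement can be required only from here on. Enrolment is planned from January 2024 to December 2025 and this version is dated January 31, 2025, so 13 of 24 months (54%) had passed. With even accrual that is about 200 x 13/24 = 108 patients, and the order of removal and AI reading may not be recoverable for all of their slides.

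### Does it matter that the accuracy, sensitivity and specificity ratios count cases without saying whether a case is a slide or a patient?

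*Protocol*

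**What the plan says.** Section V(iv) of the protocol names three indicators. Accuracy is given as "Accuracy: Ratio of the combined number of true-positive and true-negative cases predicted by the AI model to the total number of cases tested". The second, sensitivity, has the same form, and the third reads "Specificity: Ratio of negative cases identified by the AI model to the number of negative cases confirmed by the gold standard". None of them says what a case is, or whether the gold standard is set per slide or per patient.

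Section V(iii), directly before, describes how the model reaches a decision. It ends at the single whole slide image (WSI): "If the number of pixels in the cancer category within the WSI is greater than 0, classify the WSI as positive", and otherwise negative. The readable text has no step that combines the slides of one patient.

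Other places bear on the unit:

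- Section III, on what the study is for in actual practice: "To evaluate the diagnostic performance and application value of the pre-developed AI diagnostic model for prostate cancer lymph node metastasis detection".
- Section IX, benefit: "Expected to assist pathologists in reducing missed diagnosis of lymph node micrometastases".
- Section I, rationale: "accurate postoperative pathological lymph node staging holds significant implications for subsequent treatment and prognosis".
- Section VII, item 1: the plan is to "prospectively enroll about 200 consecutive prostate cancer patients".
- Section VII, item 2.2: "Approximately 10 lymph node pathology slides will be acquired from each patient", around 2,000 images in all.

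**The concern.** In ordinary clinical usage a case is often a patient, so the word can be read two ways, and the two denominators differ tenfold. The summary motivates the study by nodal staging, which is a property of the patient, and the stated purpose includes the model's value in practice. Yet the only computable reading is per slide, and no patient-level indicator is listed.

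The two levels need not agree. If a patient were called positive whenever any slide is positive, false positives would accumulate over a node-negative patient's slides, and patient specificity would fall below slide specificity. Sensitivity would tend to stay level or rise. A reader given only slide ratios could then think the model more specific for a patient's node status than it is. If the unit were truly open, it could also be chosen after the results were known.

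**Working it through.** **1. The plan's own figure.** 200 patients × 10 slides = 2,000 images, which matches the stated count. The protocol gives no target accuracy, precision or power, so there is no other figure to reproduce.

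**2. Which unit can be computed as written?** V(iv) counts results predicted by the model. The only prediction defined in V(iii) is positive or negative for one WSI. Slide counts can therefore be formed directly. Patient counts would need two further definitions: a rule combining slide labels, and a reference result per patient. Nothing in the readable text contradicts the slide reading, and sections III (detection) and IX (help in reading slides) agree with it.

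**3. How far could the two levels differ?** Every input here except the 10 slides per patient is an assumption that the protocol does not give: a rule that any positive slide makes the patient positive, the slide specificity *sp*, the within-patient correlation (ICC) of false positives from 0 to 0.3, and 140 to 180 node-negative patients among the 200.

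Patient specificity is the probability that all *m* negative slides are called negative.

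- Independent slides: sp^m.
- Correlated slides (beta-binomial): the product over j = 0 to m−1 of (a + j)/(a + b + j), with a = sp(1 − ICC)/ICC and b = (1 − sp)(1 − ICC)/ICC.

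For example, at sp = 0.995 and m = 10 with independent slides, 0.995^10 = 0.951, a gap of 99.5 − 95.1 = 4.4 points. With 180 node-negative patients, 180 × (1 − 0.951) is about 9 falsely positive patients.

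Results for m = 10, from ICC 0.3 to ICC 0. Patient counts run from 140 patients at ICC 0.3 to 180 at ICC 0.

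| Slide specificity | Patient specificity | Gap (points) | Falsely positive patients |
|---|---|---|---|
| 99.9% | 99.6–99.0% | 0.3–0.9 | about 1–2 |
| 99.5% | 97.9–95.1% | 1.6–4.4 | 3–9 |
| 99% | 95.8–90.4% | 3.2–8.6 | 6–17 |
| 98% | 91.7–81.7% | 6.3–16.3 | 12–33 |

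Varying the number of slides from 5 (ICC 0.3) to 15 (ICC 0) widens the gap to 0.2–1.4 points at 99.9% and 4.0–24.1 points at 98%.

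**4. Sensitivity under the same rule.** With *k* truly positive slides of 10, patient sensitivity = 1 − P(all *k* missed) × P(all 10 − k negative slides called negative), taking the two groups of slides as independent of each other. At an assumed slide sensitivity of 90% and slide specificity of 99.5%, this is 90.2–90.4% for k = 1 and 96.4–99.0% for k = 2.

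**5. What the arithmetic shows.** The choice of level can matter, but across these assumptions the specificity gap runs from 0.2 to 24.1 points. The protocol states none of the quantities that would place this trial in that range, and it does not state the any-positive rule either.

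**The case for a change.** The strongest case for a change is that numerator, denominator and reference are definitions the protocol itself writes down, so leaving the unit open is a fault in its own text and not a detail passed to a later document. The study enrols consecutive patients, treatment decisions follow a patient's node status, and a patient-level table needs no new data. It would cost a few words and one tabulation. Its drawback is a probably lower and less precise figure: a 95% half-width of about 2.3 to 3.7 points at patient specificities of 97.9% to 95.1% with 180 or 140 node-negative patients, against roughly 0.3 to 0.9 points for slide specificity of 99.5% on their 1,400 to 1,800 slides (design effect 1 to 1 + 9 × 0.3 = 3.7).

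Part of this stands. The word is loose, the unit of the gold standard is unstated, and patient-level results would be useful to readers.

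It does not carry the case to a change. Context settles the unit, because the model labels nothing but slides. How slides are combined within a patient, and which further levels are reported, is commonly left to the analysis plan, which may exist and is not shown. The study-design and algorithm flow charts are also unreadable here, so the absence of a patient-level step is not established. Finally, the described use is to assist pathologists, so an unreviewed any-positive call by the model is not shown to decide a patient's node status.

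**Conclusion.** No change to the plan follows. The missing unit is a gap in wording that an analyst would fill sensibly from V(iii): a case is a WSI, compared with the reference result for that WSI. On that reading the plan yields valid slide-level accuracy, sensitivity and specificity, and no stated number, rule or conclusion is wrong.

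The patient-level result is a worthwhile optional addition to the analysis plan, and it remains available later because the slides stay linked to about 200 patients. Its possible distance from the slide result, 0.3 to 16.3 points of specificity with 10 slides per patient, rests wholly on the assumed any-positive rule, slide specificity of 98% to 99.9% and ICC of 0 to 0.3. The counts of falsely positive patients also assume 140 to 180 node-negative patients. The conclusion would be different if a readable part of the protocol claimed patient-level performance from the slide ratios. None does.
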